We will test the hypothesis that TNF- α antagonism with etanercept improves the clinical response to standard of care treatment with IVIG and aspirin therapy in KD patients between 2 months and 20 years of age. To test this hypothesis we will perform a double-blinded placebo controlled trial in 196 children with KD and obtain data in order to achieve an orphan designation for etanercept.

Primary Aim

1. Determine if etanercept (0.8 mg/kg, maximum 50 mg) given subcutaneously reduces IVIG refractory rate and retreatment rate in the KD patient population. Our goal is to randomize and complete the trial in 110 patients in the etanercept treatment group and 110 patients in the placebo group.

Secondary Aims

1. Determine if the safety profile differs between the etanercept treated group and the placebo group.
2. Determine if etanercept treatment alters the rate of coronary artery dilation and disease (CAD) defined by z-scores at 2 and 6 weeks after treatment.
3. Determine the pharmacokinetics of etanercept in KD patients

3 Research Design and Methods

We propose a placebo-controlled randomized double blind multi-center study in patients, age 2 months to 20 years, with acute Kawasaki disease. All study investigators will be blinded except for pharmacists.

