3.2 Secondary Clinical Endpoints

Determine if the safety profile differs between the etanercept treated group and the placebo group.

Secondary safety endpoints will be number of adverse events, serious or otherwise within 30 days of treatment, with specific focus on serious infections, defined as “those requiring hospital admission” for treatment. The latter have been noted in patients receiving much longer courses of etanercept than proposed for this protocol, and for different diseases.

Our study will be the first to evaluate efficacy of Etanercept in reducing inflammation in an acute inflammatory disease in children, as opposed to chronic inflammatory diseases. The acute phase reactant, C-reactive protein, will be followed throughout the study as a laboratory measure of inflammation. We will also determine if etanercept modifies serum concentrations of cytokines, interleukin-3, interleukin-6, and TNF- α .

We propose the largest cohort for study of Etanercept in children performed to date.

Secondary clinical endpoints will be directed to determine if etanercept treatment alters the rate of coronary artery disease defined by z-scores at 2 and 6 weeks after treatment.

We will also determine if etanercept treatment 1) alters development of coronary artery dilation or disease in patients with normal coronaries on initial echocardiogram, 2) promotes healing of coronary artery disease, when apparent on initial echocardiogram, 3) alters treatment course by reducing total number of hospitalization days, and 4) incidence of CRP normalization by 7 days.

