Secondary outcome variables that are measured on a continuous scale include the coronary artery diameters obtained on the LMCA, pLAD and pRCA and the corresponding Z-scores (normalized for the patient's BSA) at each of those locations. Z-scores will be summarized at each time point by treatment group and the within-subject changes in Z-score relative to baseline will be summarized for the post-treatment time points (week 1 and week 5) as well. The within-subject changes in actual artery diameter will also be summarized at week 1 and week 5. Summary statistics will include the mean, SD and selected percentiles.

CONFIDENTIAL

This material is the property of the Seattle Children's Research Institute. Do not disclose or use except as authorized in writing by the study sponsor-investigator.

Change values will be summarized both overall for the treatment group as a whole and then stratified by whether or not the subject has evidence of dilation at baseline (Z -score ≥ 2.5). A Generalized Estimating Equation (GEE) model will be used to compare change values between the Etanercept and placebo groups. The GEE model is needed to accommodate adjustment for the correlation between observations obtained on the same individual at 1 and 5 weeks. Since the addition of Etanercept may have a differing magnitude of impact on change in artery diameter depending on whether the artery was dilated at baseline, terms for dilation status at baseline and the interaction between dilation and treatment group will be included in the model.

Another secondary outcome is the presence of aneurysm as defined by the Japanese Health Ministry criteria (see Echo criteria above). The pre- and post-treatment proportions of subjects in each group having an aneurysm detected will be calculated along with the exact binomial 95% confidence interval. Comparison of post-treatment aneurysm proportions will be done via a stratified Chi-square test, with strata for presence/absence of aneurysm at baseline.

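### The coronary Z-score model uses baseline only as dilated yes/no and never names its overall treatment contrast; adding the baseline Z already measured gives modest extra precision at no cost

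*Combined protocol and SAP*

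**What the plan says.** Section 7 (Statistical Design and Analysis) lists coronary diameters and Z-scores as continuous secondary outcomes and states that "A Generalized Estimating Equation (GEE) model will be used to compare change values between the Etanercept and placebo groups". The GEE is chosen to handle the "correlation between observations obtained on the same individual at 1 and 5 weeks".

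Change values are summarised overall and also "stratified by whether or not the subject has evidence of dilation at baseline", with dilation meaning Z of 2.5 or more. Because etanercept "may have a differing magnitude of impact on change in artery diameter depending on whether the artery was dilated at baseline", the model is fixed in advance: "terms for dilation status at baseline and the interaction between dilation and treatment group will be included in the model".

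Section 7 does not give the coding of dilation status, the contrast that counts as the treatment comparison, a rule for combining the two strata, or a continuous baseline covariate. No other section supplies them.

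Two related statements stand elsewhere. Section 3.2 asks whether etanercept "alters development of coronary artery dilation or disease in patients with normal coronaries on initial echocardiogram" and, separately, whether it helps existing coronary disease to heal. The second of the Secondary Aims in Section 2 is to "Determine if etanercept treatment alters the rate of coronary artery dilation and disease (CAD) defined by z-scores at 2 and 6 weeks after treatment".

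**The concern.** Two things are left loose in one model.

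First, once an interaction is always in the model, the treatment coefficient means different things under different codings of dilation. The plan promises one comparison between arms but does not define it. The sponsor itself allows that the effect may differ by baseline dilation, so the candidate estimates could differ materially, and the choice could be made after unblinding.

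Second, baseline Z predicts change in Z strongly: children with high baseline values tend to fall and those with low values tend to rise. A yes/no cut at 2.5 captures only part of that relation. The rest stays in the residual variance and widens the interval for etanercept, although the number needed to remove it is already in the database.

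**Working it through.** **Plan's own figure.** There is none to reproduce. Section 4.3 powers only the primary endpoint; no effect size, SD or power is given for the coronary model.

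**Inputs.**
- From the documents: 196 children (98 per arm, taking 1:1), dilation cut at Z of 2.5, two post-treatment visits.
- Assumed: baseline Z normal with mean 1.3 and SD 1.4, equal SD at follow-up, correlation ρ between baseline and follow-up of 0.4 to 0.75, uniform effect of 0.45 Z, one follow-up visit, two-sided 5% test.
- Dilated share p: these assumptions give c = (2.5 − 1.3)/1.4 = 0.857 and p = 0.196. Section 1.1 cites CAD at 6 weeks of 18.9% overall and 9% in those free of it at baseline. If a fraction x of baseline disease persists, p = (0.189 − 0.09)/(x − 0.09). This is 0.11 at x = 1 and 0.32 at x = 0.4, so about 20% is plausible.

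**Step 1: what the treatment term estimates.** Write mean change as a + bT + gD + hTD, with D = 1 if dilated. The effect is b in undilated children, b + h in dilated children and b + ph overall. Illustration: effects of −0.2 SD and −0.8 SD (b = −0.2, h = −0.6) and p = 0.2.

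| Coding of dilation | Treatment term equals | Value |
|---|---|---|
| 0/1 | b | −0.20 |
| −1/+1 | b + h/2 | −0.50 |
| centred at p, or weighted contrast | b + ph | −0.32 |

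A simulation with two visits, 98 per arm and ρ = 0.5 (4,000 runs) returned the same three means, with power of 29%, 91% and 73%. Adding continuous baseline Z to the centred version kept the mean at −0.32 and raised power to 80%.

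**Step 2: precision, like for like.** Compare the overall contrast from the planned model with the overall effect after adding continuous baseline Z. Residual variances, in units of SD²:
- with continuous baseline: 1 − ρ²
- with yes/no dilation only: 1 − ρ² + (1 − ρ)²w, where w = 1 − φ(c)²/[p(1 − p)]

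Here φ(0.857) = 0.276, so w = 1 − 0.0763/0.1574 = 0.515. The variance ratio is 1 + w(1 − ρ)/(1 + ρ).

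| ρ | Arithmetic | Excess variance | Simulated |
|---|---|---|---|
| 0.4 | 0.515 × 0.6/1.4 | 22% | 23% |
| 0.5 | 0.515 × 0.5/1.5 | 17% | 18% |
| 0.6 | 0.515 × 0.4/1.6 | 13% | 13% |
| 0.75 | 0.515 × 0.25/1.75 | 7% | 6% |

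At ρ = 0.6 the residual variances are 0.722 and 0.640. With SE = 1.4 × √(4v/196), the SEs are 0.170 and 0.160. Power is Φ(0.45/0.170 − 1.96) = 75% and Φ(0.45/0.160 − 1.96) = 80%; one simulation of this setting gave 74% and 78%.

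**Step 3: does the interaction cost anything?** With continuous baseline in the model, the SE is 0.160 without an interaction and 0.161 with a centred one. Dropping it gains nothing.

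**Step 4: sensitivity.** At ρ = 0.5 the excess is 22%, 17% and 14% for 10%, 20% and 30% dilated. Over ρ from 0.3 to 0.9 and those shares it runs from 35% down to 2%. The yes/no term recovers 34%, 49% and 58% of the gain that continuous baseline offers over unadjusted change. With two visits, 20% dilated, ρ = 0.5 and a uniform effect, the simulated SDs were 0.124 and 0.114; (0.124/0.114)² = 1.18, so a second visit does not remove the excess.

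**The case against.** A reader might infer that the planned treatment effect describes undilated children only. The documents do not support that. They state no coding and do not say that a single coefficient will be reported; the same fitted model yields an overall effect through a weighted contrast. What stands is that the contrast is unspecified.

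A reader might also infer that the interaction is a mistake. It is deliberate: Section 7 gives the reason, and Section 3.2 asks separately about children with and without coronary disease at baseline. For those questions the stratum effects are the requested answers, and Step 3 shows that a centred interaction costs almost nothing.

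A larger loss can be computed by setting the 0/1 coefficient (SE 0.190 at ρ = 0.6) against the continuous-baseline model (0.160), which gives (0.190/0.160)² = 1.41. That comparison mixes a subgroup coefficient with an overall effect. Only the like-for-like 13% is due to the missing covariate.

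The coronary aim in Section 2 concerns a rate, whereas this GEE models mean change, so that aim does not by itself demand an overall mean-change effect. The need for one rests on Section 7's own promise to compare the two groups.

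Finally, baseline Z is not ignored: it is subtracted in the change score, and the yes/no term recovers a third to over half of the remaining gain. Section 3.1 makes the coronary measures secondary on purpose, and no power is claimed for this model. All of this limits the size of the point. None of it supplies the missing covariate or contrast.

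**Conclusion.** The point holds in a limited form. The plan adjusts for baseline only through a cut at Z of 2.5 and does not define its overall treatment contrast. Under the most favourable reading of the planned model, adding continuous baseline Z still saves the equivalent of about 6% to 23% more patients for correlations of 0.75 to 0.4.

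That range rests on an assumed normal baseline, mean 1.3, SD 1.4, about 20% dilated and one follow-up visit; the power figures also assume a uniform effect of 0.45 Z. Only the 196 comes from the documents. A higher correlation or a larger dilated share shrinks the gain.

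The planned analysis is not biased: randomisation protects whichever contrast is named, and the primary refractoriness comparison is untouched. The gap in definition matters most if the effect really differs by baseline dilation, since the codings then give different answers. This is a free improvement to a secondary analysis.

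**What to change.** Amend the coronary paragraph of Section 7 before unblinding:

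1. Add the continuous baseline Z-score of the artery analysed as a covariate (baseline diameter for the diameter analysis), together with visit.
2. Define the overall etanercept-placebo comparison as the treatment term with the dilation interaction centred at the observed dilated share, or as the equivalent stratum-weighted contrast.
3. Keep the interaction test and the effects in dilated and undilated children as separately labelled results that serve the Section 3.2 questions.
4. State whether dilation is classified per child or per artery; Section 7 uses both wordings.

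Cost: a few sentences of SAP text and minor programming. No new data, visits or patients are needed, because the baseline measurement is already required for the change score.

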In the open-label study, the most common adverse events were injection-site reactions (39 percent of patients), upper respiratory tract infections (35 percent), headache (20 percent), rhinitis (16 percent), abdominal pain (16 percent), vomiting (14 percent), pharyngitis (14 percent), nausea (12 percent), gastrointestinal infection (12 percent), and rash (10 percent). In the double-blind study, there were no significant differences in the frequencies of adverse events between patients who received etanercept and those who received placebo. Injection-site reactions occurred in one patient in each of the treatment groups in the double-blind study. There were no laboratory abnormalities requiring urgent treatment in the etanercept group.

In an open label extension study after 4 years of treatment ⁴⁹, the rate of SAEs was 0.13 per patient-year, and the rate of serious infections was 0.04 per patient-year, in a total etanercept exposure of 225 patient-years. Serious infections included postoperative chin implant infection (n=1), wound infection (n=1), severe gastroenteritis (n=1), herpes zoster (n =1), and appendicitis (n = 1). The investigators concluded that Etanercept offered sustained benefit and an acceptable safety profile in children with JRA down to age 4 years.

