Adverse events will be tabulated for each treatment group by severity, relationship to study drug and body system affected (according to the NCI CTC grading and MEDDRA classification system). The outcome of any SAE episodes that occur will be summarized. Adverse event rates will be compared between treatment groups using Poisson or negative binomial regression modeling. The proportions of subjects experiencing an adverse event of any type and the proportions experiencing an SAE will be compared using chi-square or Fisher's Exact testing.

Pharmacokinetic analyses: PK analyses will be performed after completion of the study and unblinding, so as not to unblind study investigators. Samples from patients receiving etanercept will be forwarded to the Seattle site for storage and then later submitted to Amgen for determination of serum drug concentrations. Peak and trough analyses will be performed. Drug clearance, volume of distribution and $\frac{1}{2}$ life will be determined using etanercept modeling and algorithms⁴¹ and loaded on SAAM2 software available at the University of Washington.

CRP and other standard laboratory studies will be performed in the clinical laboratory of each participating hospital. Serum cytokines, IL-3, IL-6, and TNF α will be performed in Center of Developmental Therapeutics at Children's Hospital Research Institute in Seattle. Assay will be performed on Luminex-200 multiplex system, which resides in center.

8 Safety and Adverse Events

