8.5.1 Independent Data Monitoring Committee

The Data Monitoring Committee (DMC) will be composed of a pediatric rheumatologist, and a pediatric cardiologist to oversee the study. Safety data of the 196 patients with regards to adverse events, specifically focusing on infections, will be closely monitored in these patients

- *The DMC will meet at least once every 6 months via telephone conference.*
- *The safety data will be supplied to the DMC by the principal investigators team. .*
- *The DMC will prepare minutes to record the summary of its various meetings.*
- *The DMC will appropriately report its findings and/or recommendations to the PI and regulatory bodies.*

The Data Safety Plan and Data Monitoring Committee (DMC)

The data safety plan for this study is also included in detail in the Human Subject section. The DMC was established and chartered in order to monitor the progress of the pilot study. The DMC will continue this

PRIMARY RESPONSIBILITIES OF THE DMC

The DMC will be responsible for safeguarding the interests of trial participants, assessing the safety of the interventions during the trial, and for monitoring the overall conduct of the clinical trial. The DMC will provide recommendations about stopping or continuing the trial. To contribute to enhancing the integrity of the trial, the DMC may also formulate recommendations relating to the selection/recruitment/retention of participants, their management, improving adherence to protocol-specified regimens and retention of participants, and the procedures for data management and quality control.

The DMC will be advisory to the Principal Investigator. The Principal Investigator will be responsible for promptly reviewing the DMC recommendations, to decide whether to continue or terminate the trial, and to determine whether amendments to the protocol or changes in study conduct are required. The Principal Investigator will be required to forward all DMC recommendations to the IRB.

Members

The DMC will be an independent multidisciplinary group consisting of clinicians, whom collectively have experience in the management of patients with Kawasaki Disease and in the conduct and monitoring of clinical trials. Generally, three pediatric subspecialties deal with KD. These are cardiology, rheumatology, and infectious disease. Each of these subspecialties will be represented on the DMC.

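### Section 7 compares SAEs by a significance test with no effect estimate or interval; for uncommon SAEs and serious infections a non-significant result could not answer the safety aim

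*Combined protocol and SAP*

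**What the plan says.** The first secondary aim (Section 2, repeated in Section 3.2) is: "Determine if the safety profile differs between the etanercept treated group and the placebo group". Section 3.2 gives specific attention to serious infections, and Section 8.5.1 repeats that focus for the monitoring committee: "Safety data of the 196 patients with regards to adverse events, specifically focusing on infections".

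Section 7 sets out the safety analysis. Adverse events are tabulated by arm, severity, relationship and body system. For SAEs, "The outcome of any SAE episodes that occur will be summarized". For event rates, "Adverse event rates will be compared between treatment groups using Poisson or negative binomial regression modeling". For subjects with at least one event, "the proportions experiencing an SAE will be compared using chi-square or Fisher's Exact testing". No risk difference, ratio, confidence interval, margin or power is named for SAEs or for serious infections. In the same section, aneurysm proportions are to be "calculated along with the exact binomial 95% confidence interval", arm by arm.

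On what counts as an SAE, Section 8.1 says two things. Under hospitalization, it generally excludes admission for the target disease unless the investigator judges it a worsening, and it leaves the readmission definition to the DMC organizational meeting. Under expected adverse events, it lists readmission for recurrent or persistent fever as an expected SAE.

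**The concern.** A test on a proportion answers only whether the data are incompatible with no difference. When events are few, it is likely to be non-significant even if the true excess is large. The useful result is then how large an excess the data have and have not excluded, and a p-value does not give that.

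The trial enrols children from 2 months of age and is meant to support an orphan designation. If the SAE result is only a non-significant p-value, a reader can take it as evidence of equal safety, which it would not be. If fever readmissions are pooled into the SAE count, there is a second problem. Etanercept is expected to reduce IVIG failure, so a pooled comparison can look favourable through efficacy alone.

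**Working it through.** **Inputs**
- Arm size: 196 in total (Study Summary, Sections 4 and 8.5.1), taken as 98 per arm; 1:1 allocation is assumed. Sections 2 and 4.3 also give 110 per arm, used below as a check.
- Alpha: not stated; two-sided 0.05 assumed.
- SAE rate: the only one in the documents is in Section 1.2, where "the rate of SAEs was 0.13 per patient-year". It comes from children with juvenile arthritis in a long-term open-label etanercept extension. The same study gives 0.04 serious infections per patient-year.
- Follow-up: last dose at day 14 plus 30 days (Section 8.1), so about 44 days.
- Control SAE risk in Kawasaki disease: not in the documents, so a range is shown.

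**Plan's own figures.** There is no power figure for SAEs. The efficacy table in Section 4.3 (0.25 against 0.15, 0.10, 0.05 and 0.02) gives 270, 110, 59 and 42 per group. The two-sided 0.05, 80% power formula with continuity correction is

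n0 = [1.96·√(2·p̄(1−p̄)) + 0.842·√(p1(1−p1)+p2(1−p2))]² / d², then n = (n0/4)·[1+√(1+4/(n0·d))]².

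It returns 270, 113, 59 and 42. That is close enough to support the alpha assumption.

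**Borrowed rates turned into risks.** 1 − exp(−0.13 × 44/365.25) = 1.55% for SAEs; 1 − exp(−0.04 × 44/365.25) = 0.48% for serious infections.

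**Power of Fisher's exact test, 98 per arm.** Power is the sum of the two binomial probabilities over all tables with two-sided p ≤ 0.05.

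| Control risk | Power for a tripling | Ratio with 80% power |
|---|---|---|
| 0.5% | 0.2% | 18.6 |
| 1% | 3% | 10.6 |
| 1.55% | 10% | 7.6 |
| 2% | 16% | 6.4 |
| 3% | 32% | 4.9 |
| 5% | 57% | 3.7 |
| 10% | 93% | 2.6 |
| 25% | about 100% | 1.8 |

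At 0.48%, the ratio for serious infections is 19.3. With 110 per arm, the 80%-power ratios are 16.9 at 0.5%, 9.7 at 1% and 5.9 at 2%, and power for a tripling at 1% and 2% is 4.5% and 20%. The picture is the same.

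**What an interval adds.** With 5/98 on etanercept and 2/98 on placebo, Fisher's p is 0.44. The difference is 5.1 − 2.0 = 3.1 percentage points, and its Newcombe 95% interval runs from −2.8 to +9.5 points. The interval shows that an excess of up to 9.5 points is still compatible with the data; the p-value does not. With 0/98, the exact upper limit is 1 − 0.025^(1/98) = 3.7%.

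**If fever readmissions are counted.** Suppose readmissions are 10 against 24, other SAEs are 5 against 2, and no child has both. The pooled count is 15/98 against 26/98. The difference is −11.2 points, with a Newcombe interval of −22.4 to +0.2. The pooled upper limit looks reassuring although other SAEs are 2.5 times as frequent on etanercept.

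**The case against.** Some readers will infer more than the documents support, and the other side is right to resist.

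- *That the test can detect nothing short of about a sevenfold rise.* Sevenfold is an 80%-power threshold, not a floor: at a 1.57% control risk, a rise to 8% (about fivefold) has 44% power. It also holds only near a 1.6% control risk, which is borrowed from etanercept-treated arthritis patients and is neither a Kawasaki rate nor a placebo rate.
- *That a tripling would be missed whatever the control risk.* From 5% upward it would more often be found than missed. Section 4.3 reports that 26% of past patients needed retreatment, a rough upper guide to readmissions. If those count as SAEs, the claim reverses.
- *That the sponsor intends to read non-significance as equal safety.* No passage says so, and no equivalence claim is made. Ongoing safety decisions rest on the DMC's benefit-risk review (Sections 8.4 and 10.5), not on this test.

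The other side can add that the Poisson or negative binomial model yields a rate ratio with a standard error, so overall adverse event rates are reasonably served. The aneurysm intervals are per arm, not for the difference, and the primary endpoint has no stated interval either. Naming tests without intervals is therefore the general style of Section 7, not a lapse confined to safety. Anyone given the SAE counts could compute the interval.

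All of this stands, and it narrows the point without removing it. The rate model is not applied to SAEs or serious infections separately, and no interval is requested from it. The higher power that comes with counting readmissions does not help the safety aim, because that power concerns events that overlap the efficacy endpoint.

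**Conclusion.** The concern holds in limited form. For SAEs, Section 7 specifies a test without an estimate or interval. If non-disease SAEs occur in about 1 to 2% of controls, a non-significant result would leave roughly six- to tenfold rises as the smallest the test detects with 80% power, and the aim would go unanswered. For serious infections the position is worse, at roughly 18- to 20-fold. At a control risk of 10%, the power objection largely disappears for a tripling.

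These sizes rest on 98 per arm, 1:1 allocation, two-sided 0.05 and control risks that the documents do not give for this disease. The 1.55% and 0.48% figures also assume that the arthritis rates carry over to 44 days here. The case for separating fever readmissions does not depend on those rates. It follows from the conflict within Section 8.1 and from the overlap with the primary endpoint. This is worth correcting before unblinding, but it does not threaten the primary analysis.

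**What to change.** In Section 7, for each of (a) SAEs excluding Kawasaki fever readmissions, (b) serious infections and (c) Kawasaki fever readmissions on their own, report the risk difference with a two-sided 95% confidence interval (Newcombe or Miettinen-Nurminen) and an exact binomial interval per arm. State that a non-significant test will not be read as equal safety. The chi-square or Fisher test can stay as a supplement.

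In Section 8.1, reconcile the hospitalization paragraph with the list of expected events, so that it is fixed before unblinding whether fever readmissions count as SAEs.

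The cost is a few sentences and a few table rows. The intervals will look wide, which is a fair account of what a trial of this size can say about rare harms.
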